**A. Outcome Measure(s):**

**Aim 1:** Measured GFR by iohexol clearance and RPF by PAH clearance

**Aim 2:** Renal oxygenation by BOLD-MRI and renal perfusion by ASL-MRI

**B. Description of Population to be Enrolled:**

**Table 1: Eligibility Criteria**

Inclusion criteria	Exclusion criteria
Antibody+ T1D with <10 yr duration	Severe illness, recent DKA
Age 12-21 years	eGFR <60ml/min/1.73m  or creatinine > 1.5mg/dl or history of ACR≥300mg/g
BMI ≥ 5%ile	
Weight<350 lbs and > 57 lbs.	ACE inhibitors, angiotensin receptor blockers (ARB), diuretics, sodium-glucose co-transport (SGLT) 2 or 1 blockers, daily NSAIDs or aspirin, sulfonamides, procaine, thiazolesulfone or probenecid, atypical antipsychotics and steroids
No anemia	Anemia or allergy to shellfish or iodine
HbA1c <12%	Pregnancy or nursing
	MRI scanning contraindications (claustrophobia, implantable devices, >350 lbs)

\* Shortly after arrival to radiology unit, a MRI technician will meet with patient and/or guardian to provide preparation for the scan. This conversation will include a thorough overview including what the scanner looks like, a sample of the MRI sounds, the scan set up and the importance of lying still for the scan. The metal prescreening precaution procedure will be conducted for both patient and guardian.

**D. Description, Risks and Justification of Procedures and Data Collection Tools:**

**1. Study Duration:** The anticipated duration for the study is 2 years

**2. Duration of Participation for Each Subject:** Subject participation consists of 2 visits (~ 11 hours)

**3. Sources of Research Material:** The patient's medical record will be reviewed for diabetes diagnosis, medications, allergies and other diagnoses that may disqualify patient from participation.

**Table 6: Data to be collected during study**

Blood and Urine Samples	Blood pressures and HR
Questionnaires	Hyperglycemic clamps
DXA	Iohexol clearance
Anthropometric measurements	PAH clearance
ASL and BOLD MRI	Metabolomics

**4. Informed Consent Plan:** Appropriately qualified and informed personnel who have completed the COMIRB and HIPPA course requirements will fully explain the study protocol and consent form to the subject and guardian verbally in the language they understand. The explanation will be conducted in a quiet environment with adequate time given for the subject and guardian to review the study procedure before the commencement of the study. Asking the subject to explain the study in their own words will assess the subject's understanding. If non-English speaking subjects are enrolled in the study, the investigators will adhere to Section 10C of the COMIRB Instructions for Clinical Investigators regarding the consent of these subjects. The qualified personnel mentioned above will then obtain written consent from

the guardian and assent from the subject, co-signed on the consent form, or in subjects who are 18 years or older, direct consent. The subject and guardian will be provided a copy of the consent form for better understanding and record purposes.

5. **Special Consent/Accent Plan:** Consent will be obtained from all participants in the study. Following explanation, all subjects below 18 years old will co-sign the consent form in addition to the parents signing the consent form. All subjects age 18 or older will sign the standard consent form.
6. **Participant Compensation:** Subjects will be paid \$350 upon completion of all procedures in this study (**Table 7 below**). If the subject withdraws before the start of visit 2 (and all successive visit parts), they will still receive a \$25 gift card for completion of the screening visit. Subjects will be paid for all subsequent completed visit parts as outlined below. These payments are similar to the payments being made for each visit type in our currently ongoing adolescent studies.

**Table 7 Subject payment schedule**

Visit 1	Visit 2, Part 1Part 1	Visit 2, Part 2Part 2	Total
\$25.00	\$175.00	\$150.00	\$350.00

## 7. Potential Risks to Subjects:

Blood Samples: The collection of blood samples may result in temporary discomfort, bruising, bleeding, and on rare occasions, infection. EMLA cream helps to prevent discomfort, and sterile technique helps to minimize these risks. Nationally, the NIH Clinical Center has a guideline of 9mL/kg in 6-8 weeks for pediatric studies. Certain studies at our institution do draws over 7mL/kg in 6 weeks, or up to 7 mL/kg in a single draw but include iron supplementation. The screening visit (visit 1) will include 5 ml or less of blood (1 tsp) (HbA1c, H/E). The clamp and renal infusion studies (visit 2) includes 66mL of blood, which includes 48 mL from the clamp and 18 mL from the iohexol and PAH clearance studies. Thus, the clamp and renal infusion studies are within the more conservative pediatric CTRC guidelines of 2.5mL/kg for a single draw for pediatric studies for subjects 26 kg or greater. This is highly unlikely to exclude many subjects, as we are recruiting adolescents between ages 12 and 18 and excluding, and subjects with BMI<5% (due to potential undiagnosed illness), those groups likely to be the lightest in weight. Therefore, we will limit recruitment to subjects 26 kg or greater. In addition, by study design, subjects <5% for weight are excluded as are subjects with anemia, screened by our baseline H/H, further increasing the safety of the study regarding blood draws.

IV risks: There is temporary discomfort when the needle goes in and 10% of the time there is a small amount of bleeding under the skin that may produce a bruise. Rarely, there is a risk of a blood clot formation, infection or infiltration. EMLA cream helps to prevent discomfort and sterile technique by experienced pediatric nurses help to minimize these risks.

Hyperglycemic Clamp: To minimize the risk of any complications with the clamp, the clamp is only performed in the inpatient pediatric Clinical Translational Research Center (CTRC), by experienced personnel. To minimize this risk further, IV access is obtained prior to glucose and insulin administration, and blood sugars are monitored approximately every 10 minutes throughout the procedure and maintained at 190 mg/dL. Two IV's will be in place, in case there is a problem with one IV. If the blood glucose level is decreasing, dextrose will be given to stabilize and increase blood glucose levels. IV access will also be left in place until blood glucose values are stable after the study is completed. During the clamp, as with any IV fluids, there is also a risk of infiltration of the IV solution, which could lead to skin burn or tissue damage. During the entire clamp procedure, a pediatric CTRC nurse will remain at the bedside, and a Pediatric

Study Physician or Pediatric Nurse Practitioner will also remain at the bedside. The IV site will be continuously monitored, and the IV integrity will be noted on a check sheet.

- *Glucose injection and infusion:* Irritation of a vein resulting in phlebitis can occur with administration of concentrated glucose solutions. The risk will be decreased by minimizing the use of concentrated solutions, monitoring the veins closely during the infusion and selecting large veins for infusion of solutions.

Iohexol infusion: Iohexol (Omnipaque 300, GE Healthcare, Chicago, IL) is a nonionic, low osmolar contrast agent with a history of extensive use in Radiology practice (for contrast x-rays) that shares many qualities of an ideal GFR marker, like inulin, such as not being absorbed, metabolized, or secreted by the kidney. Low toxicity is reported in Radiology practice in children and adults in which doses that are 10-50 times higher than for GFR determination are used. In fact, for over 20 years, publications have argued that iohexol is a gold-standard measure of GFR. In contrast to some agents used to measure kidney function it is not radioactive (e.g. iothalamate renography at CHCO). The dose to be used in this study is 10-50 times less than that used in radiology studies. Our protocol has been adapted from that used by the RASS study where they reported only minor allergic reactions in over 1,200 iohexol studies performed in over 200 adults with type 1 diabetes in that study. Principal investigator, [name], has performed iohexol studies in adolescents with type 1 diabetes at Barbara Davis Center for Diabetes (62) which was well tolerated without any reactions. Furthermore, collaborator [name] has at least 10-year experience with iohexol studies in both pediatrics and adults with and without type 1 diabetes. To further limit risk of allergic reactions, patients with an allergy to iodine, seafood or iohexol will not be allowed to participate. Rare adverse effects associated with iohexol in radiology studies include cardiac arrhythmias (an irregular heartbeat), headaches, blurred vision, and nausea. To reduce risk of contamination, single use vials will be used.

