**Table 1: Eligibility Criteria**

Inclusion criteria	Exclusion criteria
Antibody+ T1D with $<10$ yr duration	Severe illness, recent DKA
Age 12-21 years	ACEi, ARB, diuretics, SGLT 2/1 blockers, atypical antipsychotics, steroids
BMI $\geq 5\text{ percentile}$	Macroalbuminuria ( $>300\text{mg/g}$ ) or eGFR $<60\text{ml/min}/1.73\text{m}^2$
Weight $<300$ lbs.	Pregnancy, nursing
HbA1c $<12\%$	Anemia or allergy to shellfish or iodine
BP $< 140/90\text{ mm Hg}$	

intrarenal hemodynamic function. They will also be provided with a 3-day diet instructions (45% carbohydrates, 30% fat, 25% protein and a goal of 3.45 g salt/day), with females studied in the follicular phase of the menstrual cycle where possible to limit impacts of nutrient and menstrual hormone variations on IR and renal function, as previously described (61). Participants will ask to administer their long

acting insulin (e.g. Lantus or Levemir) like they normally would. Patients on insulin pumps can remain on their basal rate throughout the study. If on a hybrid-closed loop (artificial pancreas), participants will be asked to open their loop for the duration of the study. The morning of the study, participants will be asked to check their blood sugar prior to arriving at the CTRC. If their blood sugar is  $\geq 250$  mg/dL, they will be asked to administer a bolus of short acting insulin using their home correction factor with a blood sugar target of 200 mg/dL.

Participants will arrive the evening before, or present fasting in the morning and have 2 IVs placed and have their blood glucose concentrations clamped in the mild hyperglycemic range (details below) (Fig 8). Baseline blood will be drawn for serum copeptin, lipids, insulin, cystatin c, creatinine, sodium, hematocrit and total protein, and iohexol and PAH boluses given via IV (see below for details). GFR and ERPF will be measured by iohexol and PAH clearance in plasma. A 4 hr urine sample will be collected to calculate ACR and AER.

**Specific methods:** Outcomes are summarized in **Table 2**. Detailed methods are listed below:

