**Figure 8 Study Protocol for SA 1**

[figure not shown]

Table 2 – Aims 1 and 2	
Primary Outcomes	Measurement Tool
Copeptin	ThermoFisher Kryptor Plus
GFR	Iohexol clearance
ERPF	PAH clearance
Renal O 2	BOLD-MRI
Renal perf.	ASL-MRI
Secondary Outcomes	
RVR	MAP/RBF (Table 3)
eGFR	Creatinine, cystatin C
Albumin excretion	Albumin-to-creatinine ratio (ACR)

**Hyperglycemic insulin clamp:** One IV will be placed in each arm to clamp the blood glucose concentrations between 170-190 mg/dL. One IV will be used to administer the boluses of iohexol and PAH in addition to a variable infusion of 20% dextrose and insulin, and the other IV will be used for blood draws. Blood glucoses will be measured every 10 minutes at the bedside, and glycemic control will be achieved using the modified and simplified insulin clamp methodology to remove glycemic effects on GFR and ERPF. The rate of insulin is adjusted based on blood specimens drawn every 10 minutes (example algorithm). Patient blood glucose (BG) levels will be checked at 8am, and adjusted to reach and maintain mild hyperglycemia up until 10am. If participant BG <70mg/dl, we will give 4 oz juice and re-test BG in 15 min. If still <70mg/dl, another 4 oz juice will be given, and BG will be re-tested 15 min later. If still <70 mg/dl,

study MD will be called, and IV D20 will be started at 100ml/hr. For BG between 70-180 mg/dL, a variable D20 infusion will be given on a sliding scale based on participant current BG and weight, as used in previous and current studies (COMIRB #13-0122, #16-1752, #18-0704). Once BG  $> 190$ mg/dl, D20 will be discontinued. If BG is not responding to changes within 2 hours or if increases above 200 mg/dl, a study physician will be contacted. Each time blood is drawn during the clamp, blood will be drawn to a clear line in the syringe to ensure there will be no IV fluid dilution and will be re-infused into the subjects after obtaining the blood sample to minimize blood loss. A blood glucose range of 170-190mg/dL (mild

hyperglycemia) was chosen to limit the acute effects of severe hyperglycemia on GFR and ERPF reproducibility, while allowing us to assess renal function in a glycemic milieu similar to the participants native

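### The 26 kg weight floor does not meet the 2.5 mL/kg blood limit it is derived from: 66 mL needs at least 26.4 kg (58.2 lb)

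*Combined protocol and SAP*

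**What the plan says.** All of the statements are in the Combined protocol and SAP.

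- **Section D, item 7, Blood Samples.** Visit 2 "includes 66mL of blood, which includes 48 mL from the clamp and 18 mL from the iohexol and PAH clearance studies". The paragraph concludes that this is within the more conservative CTRC "guidelines of 2.5mL/kg for a single draw for pediatric studies for subjects 26 kg or greater". It then sets the criterion: "Therefore, we will limit recruitment to subjects 26 kg or greater". The same paragraph allows up to 5 mL at screening and notes that "the NIH Clinical Center has a guideline of 9mL/kg in 6-8 weeks for pediatric studies". It adds that "by study design, subjects <5% for weight are excluded as are subjects with anemia, screened by our baseline H/H".
- **Section B, Table 1.** The weight criterion is "Weight<350 lbs and > 57 lbs".
- **Section IV, Table 1.** This shorter copy gives only an upper weight limit.
- **Section IV, Hyperglycemic insulin clamp.** At each clamp draw, blood is drawn to clear the line and "will be re-infused into the subjects after obtaining the blood sample to minimize blood loss".

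**The concern.** The 26 kg floor was not chosen on general grounds. The text derives it from a volume of 66 mL and a limit of 2.5 mL/kg, so it can be checked directly. A minimum weight that enforces a maximum volume per kilogram has to be rounded up. Rounded down, it admits the people it is meant to keep out.

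What is at stake is the accuracy of an eligibility number and of a safety statement that covers minors. The statistical design is not involved. The floor is also expressed differently in different places (26 kg, more than 57 lb, or absent), so site staff could apply different thresholds depending on which table they use.

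**Working it through.** **Inputs**

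- Visit 2 volume: 48 mL (clamp) + 18 mL (iohexol and PAH) = 66 mL. The components add up to the stated total (section D, item 7).
- Limit: 2.5 mL/kg for a single draw (same paragraph).
- Stated floors: 26 kg (section D, item 7) and more than 57 lb (section B, Table 1).
- Conversion: 1 lb = 0.45359 kg.

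**Step 1. Try to reproduce the stated floor.** Minimum weight = volume / limit = 66 / 2.5 = 26.4 kg, and 26.4 / 0.45359 = 58.2 lb. The stated 26 kg appears only if 26.4 is rounded to the nearest kilogram. Other readings of the volume do not give it:

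- clamp blood alone: 48 / 2.5 = 19.2 kg
- clearance blood alone: 18 / 2.5 = 7.2 kg
- visit 2 plus screening: 71 / 2.5 = 28.4 kg

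**Step 2. Evaluate the draw at each candidate floor.** The allowed volume is weight × 2.5, and the dose is 66 / weight.

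| Weight | kg | Allowed at 2.5 mL/kg | 66 mL as mL/kg | Excess over limit |
|---|---|---|---|---|
| 57 lb | 25.85 | 64.6 mL | 2.55 | 1.4 mL (2.1%) |
| 26 kg (57.3 lb) | 26.00 | 65.0 mL | 2.54 | 1.0 mL (1.5%) |
| 58 lb | 26.31 | 65.8 mL | 2.51 | 0.2 mL (0.3%) |
| 26.4 kg (58.2 lb) | 26.40 | 66.0 mL | 2.50 | none |
| 59 lb | 26.76 | 66.9 mL | 2.47 | none |
| 27 kg (59.5 lb) | 27.00 | 67.5 mL | 2.44 | none |

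**Step 3. Affected band.** The section B table excludes 57 lb itself, and section D, item 7 separately requires 26 kg. Read together, they let in participants from 26 to 26.4 kg who exceed the limit. The largest excess is 1.0 mL. The 57 lb row shows only where the table's wording sits if it is used alone.

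**Step 4. Alternative of reducing the volume.** With 65 mL at visit 2, 65 / 26 = 2.50 mL/kg, so the 26 kg floor holds exactly. At 58 lb, 65 / 26.31 = 2.47 mL/kg.

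**Step 5. Against the looser guideline.** Both visits together take 5 + 66 = 71 mL. At 26 kg this is 71 / 26 = 2.73 mL/kg, and 2.73 / 9 = 30% of the 9 mL/kg that the protocol cites.

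**The case against.** The strongest reply is that this is a rounding difference of no consequence. The limit is given to one decimal, and 2.54 is 2.5 at that precision. The CTRC guideline itself is not in the documents, so one cannot see how it treats rounding, or whether a single draw is meant to cover serial samples over several hours. Clamp draws include re-infusion to limit loss. The cited 9 mL/kg guideline is far from being reached. The population is 12-21 years old, with anemia and BMI below the 5th percentile excluded, and the risk paragraph adds an exclusion for weight below 5%. No participant is shown to be affected.

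Most of this stands as a statement about size. The documents give no weight distribution, so the number of participants in the 0.4 kg band cannot be computed, and it may well be zero. It does not rescue the statement as written:

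- The risk paragraph sets the full 66 mL against 2.5 mL/kg and treats the result as compliance, so its own reading of the limit is the one to apply.
- It deducts nothing for re-infusion, and the documents do not say whether the 48 mL is already net of it.
- Compliance is claimed with the 2.5 mL/kg limit, so room under the 9 mL/kg guideline does not make that claim true.
- The weight-percentile exclusion is in neither eligibility table; both list only BMI.

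A further fair point is that the visit description in section IV has fasting blood drawn before the clamp (copeptin, lipids, insulin and others). The risk paragraph itemises only clamp and clearance blood and does not say where that draw is counted. The 66 mL should be confirmed before a new floor with a narrow margin is fixed.

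**Conclusion.** The concern holds. On the protocol's own inputs the floor should be 26.4 kg (58.2 lb). A floor of 26 kg allows a draw of 2.54 mL/kg, 1.0 mL or 1.5% over the stated limit. The eligibility number and the compliance statement are both wrong as written.

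The effect is very small: a 0.4 kg band, few if any participants, and no change to any endpoint, analysis or power figure. It is a minor correction. The conclusion assumes that 66 mL is the volume to be compared with the limit, as the protocol itself does, and that 2.5 mL/kg is a ceiling.

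**What to change.** First confirm that the 66 mL includes the fasting draw, and state whether it is net of re-infused blood. If 66 mL stands, choose one of the following:

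1. **Raise the floor** to at least 26.4 kg in section D, item 7 and in the section B eligibility table. In whole units that means at least 59 lb (2.47 mL/kg) or at least 27 kg (2.44 mL/kg).
2. **Cap visit 2 blood at 65 mL** and keep a true 26 kg floor, written in the table as at least 58 lb (65 mL gives 2.47 mL/kg).

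Copy the chosen floor into the section IV version of Table 1, so that every statement of eligibility carries the same number. The cost is one corrected number in two places and one addition to a table, with almost no participants excluded.

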Magnetic Resonance Imaging (MRI): The MRI is a non-invasive scan of the renal arteries. MRI uses a magnet and there is no radiation involved with the MRI. The scan may be loud; therefore, the subject is provided with audio protection and optional television. Due to the magnet, subjects with implanted metal devices will be excluded. Some people feel claustrophobic in small spaces, and if this occurs the MRI will be stopped. Incidental findings on MRI will be relayed to ordering physician and/or PCP.

A small single dose of furosemide will be injected intravenously to obtain BOLD MRI before and after injection. The dose of furosemide (20mg) is below the typical 1-2 mg/kg dose used clinically in pediatrics. Potential side effects include excessive diuresis (increased discharge of urine), low potassium (leading to symptoms like dry mouth, excessive thirst, weak or irregular heartbeat, muscle pain or cramps), stomach upset, dizziness, muscle weakness, low blood pressure with change of position, hyperglycemia, jaundice, rash, sensitivity to the light, ringing or buzzing noises in the ears. All these while considered possible are very rare following a single low dose of 20 mg. After the Furosemide injection, participants will receive IV fluids during the clamp and will remain well hydrated. All participants will be asked to drink 500mL of water with their study lunch, and therefore ensure adequate hydration of all subjects. A study physician and/or nurse will be present during the injection.

Physical Exam, urine samples and anthropomorphic measures: There are no known risks associated with the physical exam, urine samples, or anthropomorphic measures.

Confidentiality: Violation of privacy and loss of confidentiality are both risks to which research participants are exposed. The possibility of these risks increases when protected health information is collected. Every effort will be made to decrease this risk by limiting access to protected health information, storing this information in a password protected database, and identifying subjects only by a unique identifier that is kept in a separate location in a locked container, traceable only by study personnel. All tests involve risk of identifying asymptomatic/subclinical abnormalities. The study may also include risks that are unknown at this time of examination.

## **8. Plan to minimize risk / protection against risk:**

The hyperglycemic clamps, iohexol and PAH infusions are standard procedures used in several research studies and settings, including our RENAL-HEIR protocol (COMIRB #16-1752) and IMPROVE-T2D protocol (COMIRB #18-0704). Adverse events are uncommon when the procedure is done by experienced personnel in an appropriate setting. There have been no Serious Adverse Events (SAE) in the research group's experience in the Pediatric Clinical and Translational Research Center with insulin clamps, iohexol or PAH clearance studies. Therefore, we do not anticipate encountering SAEs. However, we have defined the following as possible SAEs for the purposes of monitoring: infection related to blood draw or IV placement. In addition, allergic reactions to iohexol or PAH requiring intervention (e.g. oral Benadryl) would also be considered a SAE. The PI will report serious adverse events, and any decision to suspend or halt the protocol to the CTRC and COMIRB immediately. The subject will also be instructed to report the event to their PCP.

All investigators are currently certified in the Colorado IRB and HIPAA regulatory courses required to perform human subject research at the University of Colorado Denver and the Children's Hospital Colorado and will be required to maintain such certification throughout the study. No protected health information will be collected until the appropriate HIPAA forms are completed. This information will be accessible only by the study investigators, Federal agencies overseeing human subject research, the Colorado Multiple Institutional Review Board, regulatory officials from the institution where the research is being conducted to monitor safety and compliance with policies. Every effort will be made to decrease the risk of loss of confidentiality by limiting access to protected health information, storing this information in a password protected database, and identifying subjects only by a unique identifier that is kept in a separate location in a locked container, traceable only by study personnel. Electronic Data will be stored in a password protected database and file servers. Paper files will be stored in a locked cabinet in the office of the Principal Investigator, accessible only to study investigators.

